#### 4.2 SCIENTIFIC RATIONALE FOR STUDY DESIGN

The control group will be randomized to receive the standard-of-care pressure dressing that includes coverage of the sutured incision with sterile gauze and non-penetrable barrier (e.g., Tegaderm™) consistent with the national standard for dressing Cesarean section incisions. These dressings are removed on postoperative day #1 as per standard protocol.

The control dressing will be the current standard of care pressure dressing that is used on all patients undergoing cesarean delivery. There are no known or potential problems associated with the control group. All other interventions will be as per current protocol.

The study design is a superiority randomized controlled trial (RCT) because the aim is to show that the PICO NPWT is superior to the standard pressure dressing in regards to incidence of SSIs and SSOs.

#### 4.3 JUSTIFICATION FOR DOSE

Not applicable.

#### 4.4 END OF STUDY DEFINITION

A participant is considered to have completed the study if she has completed all phases of the study including the last visit or the last scheduled procedure shown in the Schedule of Activities (SoA), Section 1.3.

## 5 STUDY POPULATION

We will recruit obese women undergoing elective cesarean section. Subjects who consent will be randomized to use either the PICO NPWT or standard of care dressing.

Females aged  $\geq 18$  years with  $\text{BMI} \geq 35 \text{ kg/m}^2$  who are able to provide consent and are undergoing a planned cesarean delivery using subcuticular skin closure technique at the Long Island Jewish Medical Center.

Screening procedures will not be performed under a separate screening consent form.

### 5.1 INCLUSION CRITERIA

In order to be eligible to participate in this study, an individual must meet all of the following criteria:

1. Provision of signed and dated informed consent form
2. Stated willingness to comply with all study procedures and availability for the duration of the study; willing and able to return for all scheduled and required study visits
3. Female, aged 18 – 55 years
4.  $\text{BMI} \geq 35 \text{ kg/m}^2$  in the 42 days prior to surgery
5. In good general health as evidenced by medical history with a 24 – 41 weeks gestational age pregnancy scheduled for cesarean delivery for any routine indication (repeat procedure, breech presentation, abnormal placentation, uterine anomaly, maternal medical condition, or elective)
6. Ability to and willingness to adhere to the PICO negative pressure wound therapy regimen
7. Surgical skin site preparation with chlorhexidine gluconate solution (ChloraPrep©)
8. Received preoperative surgical prophylaxis antibiotics as per protocol
9. Surgical incision that can be covered completely by the NPWT skin system
10. Pre-operatively assessed to undergo a procedure with a CDC Wound Classification of:
  - a. Class I (Clean): An uninfected operative wound in which no inflammation is encountered and the respiratory, alimentary, genital, or uninfected urinary tract is not entered  
- OR -
  - b. Class II (Clean Contaminated): An operative wound in which the respiratory, alimentary, genital, or uninfected urinary tract are entered under controlled conditions and without unusual contamination
11. Wound hemostasis has been achieved

### 5.2 EXCLUSION CRITERIA

An individual who meets any of the following criteria will be excluded from participation in this study:

1. Cesarean delivery before fetal viability (24 0/7 weeks gestational age)
2. Unplanned Cesarean delivery

3. Fetal death
4. Known allergic reactions to components of the PICO NPWT system
5. Systemic bacterial or fungal infection at the time of surgery
6. Diagnosis of systemic or remote-site skin infections at time of delivery
7. Treatment with another investigational drug or other intervention within 7 days prior to cesarean delivery or 42 +/- 10 days after cesarean delivery
8. Delivery for suspected intrauterine infection (defined as maternal fever plus one clinical criteria)
9. Critical illness or immune-compromising disease (eg acquired immunodeficiency syndrome)
10. Chronic steroid use
11. Pre-operatively assessed to have a CDC Wound Classification of:
  - Class III (Contaminated): Open, fresh, accidental wounds, and/or major breaks in sterile technique or gross spillage from the gastrointestinal tract
    - OR -
  - Class IV (Dirty-Infected): Old traumatic wounds with retained devitalized tissue and those that involve existing clinical infection or perforated viscera
12. High-risk for anesthesia (American Society of Anesthesiologists [ASA] class P4 – P6)
13. Intra-operative hemorrhage requiring blood transfusion, disseminated-intravascular coagulopathy (DIC) or any other medical or surgical condition during the Cesarean section deemed by the investigator to pose a prohibitively high risk for surgical re-exploration
14. Life expectancy of < 12 months
15. Unable to speak or understand English, with no interpreter available

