### PICO specifics from manufacturer product safety data sheet:

Dressing: Laminate of silicone/acrylic adhesive coated polyurethane films to polyethylene layer and polyacrylate/cellulose airlaid layer. A polyurethane port and an acrylic copolymer/nylon filter membrane are bonded to the laminate using acrylic adhesive. PVC tubing is also bonded to the polyurethane port using an acrylic adhesive. Laminate is placed on HDPE handles.

Secondary fixation strips: Laminate of acrylic adhesive coated on polyurethane film placed between polyethylene, polypropylene and paper carriers.

Pump: Internal components consist of PCBA (Printed Circuit Board Assembly consisting of multiple electronic components, PCB and soldered joints), electric motor driven diaphragm pump, air manifold (thermoplastic elastomer), wiring, connections and steel battery contacts. External components consist of 2 case halves (ABS thermoplastic), air inlet connection (ABS thermoplastic), button (thermoplastic elastomer), lenses (polystyrene) and battery cover (ABS thermoplastic).

A 10 x 30cm PICO dressing size fits most cesarean section incisions, and larger and smaller sized dressings are available.

The standard pressure dressing is composed of Telfa®, a non-adherent wound dressing which consists of absorbent cotton fibers impregnated with polyhexamethylene biguanide enclosed in a sleeve of thermoplastic polymers, cotton 4" x 4" sterile mesh gauze manufactured by Medtronic (Minneapolis, MN, USA) and a non-penetrable barrier (e.g., tape or Tegaderm™ adhesive film (3M, USA).

Figure 1:

Figure 2:

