## 8.2 SAFETY AND OTHER ASSESSMENTS

Sequence of events that will occur during screening process:

1. Review of scheduled cesarean delivery schedule for the day.
  - a. Screening procedures must be performed within 10 days of study enrollment.
2. Review of medical charts to assess for eligibility (see below).
3. Approach patient and explain trial and interventions.
4. No dietary or activity considerations are required for participation in the trial; however, patients will be counseled that the PICO dressing protocol requires the dressing to be in place for a minimum of 5 days.
5. Assessment of ability to comply with study intervention.
6. Obtain consent.
7. The patient will not be randomized until presentation to labor and delivery and randomization group will not be exposed to healthcare team until as close as possible to the end of the surgical procedure.

Information that will be obtained through review of existing data (i.e. patient's medical chart):

- Age
- BMI (kg/m^2)
- Medical comorbidities
- Pregnancy history (term, preterm, abortions, and living history)
- Mode of prior deliveries, if applicable
- Indication for cesarean delivery
- Incision assessment information from residents and attendings at follow-up visits

No study specific procedures will be performed and so no results will be provided to patients.

List and description of the following procedures/evaluations, as applicable:

- **Physical examination:** height and weight, fundal height, fetal heart rate measurement (initial study day prior to administration of intervention, and incision assessment).
- **Vital signs:** temperature, pulse, and blood pressure.
- **Assessment of adverse events.** Adverse events will be followed by attending physicians and research PI [name]. There are minimal expected adverse events that are not beyond the potential adverse events that could occur from the regular standard dressing (i.e. dressing tape site reaction or allergy to tape)

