### 9.3 POPULATIONS FOR ANALYSES

The primary statistical analysis will be based on a modified intention-to-treat (participants who underwent surgery and received the intervention). All subjects will be analyzed according to the intention-to-treat [ITT] principle. A patient will be considered evaluable and will be included in the intention-to-treat analysis if the patient has completed all phases of the study including the last visit of the last scheduled procedure in the schedule of activities, i.e. the final study visit 4—day 42±10 days post-op. Analyses that take into account the actual treatment received (e.g. use of PICO NPWT dressing for a minimum 5 days) will be carried out as a secondary analysis (per protocol [PP] analysis).

This was chosen to avoid various misleading artifacts that can arise in intervention research such as non-random attrition of participants from the study or crossover. Subjects strayed from the protocol (for instance, by not adhering to the prescribed timing of intervention, or by withdrawing from the study) will still be analyzed in the group to which they were assigned. We want to estimate the effects of using a PICO dressing at all in practice, not the effects in the subgroup of the participants who adhere to it. If patients receive a different type of dressing (intervention) accidentally from the one they were assigned, they will be excluded from the study in order to remove any bias that could arise from reasons why a provider chose to use that specific dressing instead of the assigned dressing.

In addition, a per-protocol analysis dataset will be analyzed (entire control group and PICO group who used the PICO NPWT dressing for a minimum of 5 days).

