#### 9.4.2 ANALYSIS OF THE PRIMARY EFFICACY ENDPOINT(S)

Primary endpoint: the incidence of postoperative surgical site occurrences (SSOs) post cesarean delivery. SSOs include:

- Unanticipated local inflammatory response – measured by redness, tenderness, warmth, or induration on exam. This is a binary nominal categorical variable that will be measured as a repeated measure.

- Prolonged drainage – measured as drainage from surgical skin site  $\geq 3$  days from time of surgery. This is a binary nominal categorical variable that will be measured as a repeated measure.
- Fluid collection – measured as need for skin opening to drain fluid collected (seroma) underneath the skin wound. This is a binary nominal categorical variable that will be measured as a repeated measure.
- Dehiscence – measured as opening of skin wound  $\geq 2$ mm. This is a binary nominal categorical variable that will be measured as a repeated measure.
- Surgical site infection (SSI) - measured by redness, tenderness, warmth, or induration on exam with subject fever or purulent drainage. This is a binary nominal categorical variable that will be measured as a repeated measure.

The results of statistical procedure(s) will be presented as odds ratios with 95% confidence intervals, and number-needed-to-treat.

Missing data will be handled (e.g., type of imputation technique, if any, and provide justification), and approach to handling outliers, nonadherence and lost to follow-up by reporting this data as missing (and the reason why) and including all available data in the analysis.

---

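### Exclusion 4 screens for known allergy to PICO components only, so a woman known to react to a component found only in the standard dressing can be randomised to it (minor).

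*Protocol*

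**What the plan says.** Section 5.2, item 4, excludes "Known allergic reactions to components of the PICO NPWT system". None of the other 14 exclusions and none of the 11 inclusions in section 5.1 mentions allergy to the standard dressing.

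Section 6.2.2, in the product details, lists the materials of both dressings. The contact layer of the standard dressing is "absorbent cotton fibers impregnated with polyhexamethylene biguanide enclosed in a sleeve of thermoplastic polymers". It is covered with gauze and "a non-penetrable barrier (e.g., tape or Tegaderm" film. The PICO dressing is described as "Laminate of silicone/acrylic adhesive coated polyurethane films to polyethylene layer and polyacrylate/cellulose airlaid layer", and its fixation strips are acrylic adhesive on polyurethane film. PHMB is not among the PICO materials listed.

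Section 8.2 expects few adverse events, none beyond what the regular dressing could cause, and gives as its example "dressing tape site reaction or allergy to tape".

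Section 9.4.2 defines the first component of the primary endpoint: "Unanticipated local inflammatory response – measured by redness, tenderness, warmth, or induration on exam". It makes no exception for a reaction to the dressing.

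Section 8.1 has the standard dressing removed on postoperative day 1. The schedule in section 1.3 places an incision assessment on the same day.

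**The concern.** In a two-arm comparison of dressings, a known contraindication to either one should be screened for before randomisation. Here it is screened for on one side only. Women known to react to PICO never enter. Women known to react to something found only in the standard dressing do enter, and under 1:1 allocation half of them are expected to receive it.

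The primary endpoint can be met by a sign that a contact reaction produces. Local redness on examination is one of the listed measures, and it is looked for on the day the control dressing comes off. If such redness is scored, it adds SSO events to control with no counterpart among known PICO reactors. The difference would then favour PICO for a reason unrelated to negative pressure.

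The gap looks overlooked rather than weighed. Section 4.2 states that the control group has no known or potential problems, yet section 8.2 names a tape reaction as something the regular dressing can cause.

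**Working it through.** **Step 1: reproduce the plan's figure.** Section 9.2 assumes 18% SSO on control, 8% on PICO, alpha 0.05 and 80% power.

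- Two-sided test, pooled variance, no continuity correction: 177 per group, against 180 stated.
- Power with 180 per group: 0.808.
- Odds ratio: (0.08/0.92)/(0.18/0.82) = 0.396, as stated.
- Attrition: 180/0.90 = 200 per group, as stated.

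The stated figures stand, and nothing below alters them.

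**Step 2: which women pass through the gap.**

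- *PHMB.* Listed for the standard dressing and not for PICO. Exclusion 4 does not reach it.
- *Tape or film adhesive.* PICO also carries acrylic adhesive, so exclusion 4 may already remove some women with adhesive allergy. Only those reacting to an adhesive that PICO does not share get through.

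**Step 3: size on the control rate.** The protocol gives neither the share of such women (a) nor the probability that one assigned to control is scored with redness (r). Both are assumptions. Only women who would not otherwise have had an SSO add an event, so

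increase = (1 − 0.18) × a × r, and extra events per 180 = 180 × increase.

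**Step 4: effect on the test.** Suppose the true SSO rate is 18% in both arms with 180 per arm, and the control rate is inflated as above. Let d be the inflation, SE0 the pooled standard error and SE1 the unpooled one. The chance of a significant result favouring PICO is 1 − Φ((1.96 × SE0 − d)/SE1). Without inflation it is 2.5%.

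| a (assumed) | r (assumed) | Increase in control rate | Extra events per 180 | Chance of false result favouring PICO |
|---|---|---|---|---|
| 0.5% | 50% | 0.82 × 0.005 × 0.5 = 0.2 points | 0.4 | 2.8% |
| 0.5% | 100% | 0.4 points | 0.7 | 3.2% |
| 1% | 50% | 0.4 points | 0.7 | 3.2% |
| 1% | 100% | 0.82 × 0.01 × 1 = 0.8 points | 1.5 | 3.9% |
| 2% | 100% | 1.6 points | 3.0 | 5.9% |
| 5% | 100% | 4.1 points | 7.4 | 16.1% |

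Worked line for a = 1%, r = 100%: d = 0.0082 and both standard errors are about 0.0409, so (1.96 × 0.0409 − 0.0082)/0.0409 ≈ 1.76, with upper tail 3.9%.

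The first four rows are the working range. The last two show how far the assumptions must be pushed before the effect becomes material.

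**The case against.** The case for leaving the criterion alone has several parts.

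- **The barrier is not fixed.** Tape and film are given as examples, and section 6.1.1 says standard care is not limited to them. A woman allergic to one can be given another and still receive the assigned dressing. This stands, and it leaves PHMB as the main component at issue.
- **Allergies may overlap.** Acrylic adhesive is in PICO too, so exclusion 4 may already catch many adhesive reactors. This stands, and it lowers the assumed share.
- **The endpoint component is named unanticipated.** A reaction to a known allergen is arguably anticipated, and tape-site redness need not be at the incision. This is fair, but the measure itself is "measured by redness, tenderness, warmth, or induration on exam", with no instruction to set such cases aside. The point is open, not settled.
- **Control wear is short.** The dressing comes off on day 1 under section 8.1, and section 6.1.1 allows the barrier up to two days. The next incision check is at days 7 to 14, so redness may have gone by then. This stands for later visits but not for the day 1 check.
- **PICO skin reactions also count.** Section 2.3.1 expects reddening or sensitisation no more often than with standard dressings, and PICO is worn for longer. Previously unknown reactions could therefore favour control. This stands: the one-directional argument applies only to known reactors.

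A reader might also infer that section 9.3 would drop allergic women from control alone once staff changed their dressing. The text does not support that. It reads "If patients receive a different type of dressing (intervention) accidentally from the one they were assigned, they will be excluded from the study", and a deliberate change for allergy is not accidental. Nor is a different tape plainly a different type of dressing. The stated rationale, about why a provider chose another dressing, blurs the rule but does not make it a control-only removal.

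**Conclusion.** The asymmetry is certain from the text; its effect is not. Exclusion 4 covers one dressing, the other has at least one listed component that PICO lacks, and the primary endpoint can be met by redness with no exception for contact reactions. Bias from this source would favour PICO.

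The size rests on two assumptions the protocol does not supply. With 0.5% to 1% of women affected and 50% to 100% of them scored, the control rate rises by about 0.2 to 0.8 points (0.4 to 1.5 events per 180). Use of another barrier, or overlap with PICO allergy, would reduce this. The planned 180 evaluable and 200 recruited per group are unaffected.

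A reader might infer a much larger distortion by taking 3% of women, all scored: 0.82 × 3% = 2.5 points, a quarter of the 10-point target difference. That figure needs a higher share, certain scoring, no substitution of the barrier and no overlap. The protocol supports none of these. Nor does it show that staff would ignore a charted allergy, since section 8.2 has charts reviewed at screening.

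This is a minor point, worth correcting because the correction is nearly free.

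**What to change.** In section 5.2, make item 4 symmetric: "Known allergic reactions to components of the PICO NPWT system" followed by *or of the standard dressing*. Carry the same wording to the screening form, so that the materials named in section 6.2.2 for both dressings are checked. Every randomised woman can then receive either dressing.

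The cost is one line in the protocol and one on the form. The check fits the chart review already planned in section 8.2. A few otherwise eligible women would not be enrolled: at an assumed 0.5% to 1%, about 2 to 4 of 400 (0.005 × 400 = 2; 0.01 × 400 = 4). No sample-size or analysis text has to change.

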## 7.2 PARTICIPANT DISCONTINUATION/WITHDRAWAL FROM THE STUDY

Participants are free to withdraw from participation in the study at any time upon request.

An investigator may discontinue or withdraw a participant from the study for the following reasons:

- Significant study intervention non-compliance
- If any clinical adverse event (AE), or other medical condition or situation occurs such that continued participation in the study would not be in the best interest of the participant
- Disease progression which requires discontinuation of the study intervention
- If the participant meets an exclusion criterion (either newly developed or not previously recognized) that precludes further study participation
- The PICO device is not compatible with MRI and cannot be taken in to an MRI suite. If the patient requires MRI, the PICO dressing will need to be discontinued

The reason for participant discontinuation or withdrawal from the study will be recorded. Subjects who sign the informed consent form and are randomized but do not receive the study intervention may be replaced. Subjects who sign the informed consent form, and are randomized and receive the study intervention, and subsequently withdraw, or are withdrawn or discontinued from the study, will be replaced.

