### 9.4 STATISTICAL ANALYSES

#### 9.4.1 GENERAL APPROACH

Descriptive statistics (e.g. means, standard deviations or medians and interquartile range for continuous data; frequencies and percentages for categorical data) will be calculated for the patients who meet the final inclusion/exclusion criteria.

For descriptive purposes, the overall crude estimates of the incidence of any SSO or any SII will be calculated. These incidences will also be expressed per 100 or 1,000 or 10,000 patients. The chi-square test or Fisher's exact test will be used to compare the crude incidence rates of any SSO or any SII between study groups (NPWT vs. SOC).

For continuous and ordinal variables, data will be expressed as a median with interquartile range. For dichotomous variables, percentages will be calculated. Comparisons will be performed with the Mann-Whitney test for continuous variables as appropriate. Comparisons of percentages will be performed with the Fisher Exact test as appropriate.

The incidence of SSI and SSO per 100 patients between groups will be compared. Risk ratios (RR), 95% CIs and p values assuming a 5% significance level will be presented.

For the primary outcome, the number needed to treat and absolute risk reduction will be calculated from the RR. While we do not anticipate differences between groups in terms of known or unknown prognostic factors because of randomization, adjusted analyses using multivariate logistic regression models will be used if any difference in prognostic variables is detected.

Covariates will be prespecified:

- Medical comorbidities
  - Hypertension (pregestational and gestational)
  - Diabetes (pregestational and gestational)
  - HIV
- Smoking status
- Prior cesarean delivery
- Steroid exposure (betamethasone) within 2 weeks of surgery
- Need for preoperative hair removal (particularly shaving)

Checks of assumptions (e.g., normality) underlying statistical procedures will be performed and whether any indicated corrective procedures will be applied (e.g., transformation or nonparametric tests).

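### Exclusion 7 runs through follow-up and section 7.2 allows withdrawal for a newly developed exclusion, so eligibility can act after randomisation in a way that may depend on outcome and arm

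*Protocol*

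**What the plan says.** **Eligibility (Protocol 5.2).** Item 7 excludes "Treatment with another investigational drug or other intervention within 7 days prior to cesarean delivery or 42 +/- 10 days after cesarean delivery". Item 9 excludes "Critical illness or immune-compromising disease (eg acquired immunodeficiency syndrome" and so on, with no reference time. Item 5, by contrast, is tied to a moment: "Systemic bacterial or fungal infection at the time of surgery". Item 6 is likewise tied to delivery.

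**Randomisation and blinding (4.1, 6.3).** Women are randomised in the operating room at the start of the procedure. Neither they nor the physicians are blinded.

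**Withdrawal (7.2).** The list of grounds opens with "An investigator may discontinue or withdraw a participant from the study for the following reasons" and includes "If the participant meets an exclusion criterion (either newly developed or not previously recognized) that precludes further study participation". Women who received the intervention "and subsequently withdraw, or are withdrawn or discontinued from the study, will be replaced".

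**Analysis set (9.3).** "A patient will be considered evaluable and will be included in the intention-to-treat analysis if the patient has completed all phases of the study", through the visit at day 42 +/- 10. The same section says that women who depart from the protocol, withdrawal included, are still analysed in their assigned group.

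**The concern.** An eligibility criterion should be settled before allocation. Part of item 7 cannot be, because it looks forward over the whole follow-up period, which is also the period in which SSOs are counted. Section 7.2 expressly carries the exclusion list past randomisation, and the decision lies with staff who know the arm.

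If a woman with a serious wound complication is withdrawn on this ground, replaced, and then treated as not evaluable, her event disappears and a new recruit fills her place. Replacement restores the headcount but not the event. Losing control-arm events hides a benefit; losing PICO-arm events exaggerates one. Loss in both arms lowers the event rates and the power.

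A statistical analysis plan could settle who is analysed. It could not recover outcomes that were never collected because follow-up had ended.

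**Working it through.** **1. The chain in the text.**

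| Step | Source | What it does |
|---|---|---|
| a | 5.2 item 7 | Exclusion can be met up to day 42 +/- 10 |
| b | 5.2 item 9 | Critical illness, no reference time |
| c | 6.3 | Allocation occurs in the operating room, before the post-delivery part of (a) can be known |
| d | 7.2 | A newly developed exclusion that precludes further participation is a ground for withdrawal; discretionary |
| e | 7.2 | Treated women who are withdrawn are replaced |
| f | 9.3, evaluability sentence | Not completing visit 4 means not in the intention-to-treat analysis |
| g | 9.3, later sentence | Women who withdraw are analysed as assigned |

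Steps (a) to (f) join up. Step (g) contradicts (f), so the protocol does not determine whether the event is lost from the analysis.

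**2. The plan's own figures.** Section 9.2 uses 18% v 8%, alpha 0.05 and 80% power. Sidedness is not stated; two-sided is assumed here. With mean proportion 0.13,

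n = [1.96 x sqrt(2 x 0.13 x 0.87) + 0.842 x sqrt(0.18 x 0.82 + 0.08 x 0.92)]² / 0.10² = 176.4, so 177 per group.

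The plan states 180, which gives power 0.808, and 180/0.90 = 200. The odds ratio is (0.08/0.92)/(0.18/0.82) = 0.396. The sample size reproduces and is not at issue.

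**3. How many lost events matter at the planned effect.** Expected events are 180 x 0.18 = 32.4 and 180 x 0.08 = 14.4, taken as 32 and 14. Pearson chi-square without continuity correction, removing control women with events from numerator and denominator together:

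| Control events lost | Control | PICO | p |
|---|---|---|---|
| 0 | 32/180 | 14/180 | 0.0045 |
| 1 | 31/179 | 14/180 | 0.006 |
| 4 | 28/176 | 14/180 | 0.017 |
| 7 | 25/173 | 14/180 | 0.046 |
| 8 | 24/172 | 14/180 | 0.062 |

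Eight of 32 is a quarter of the control events. If every withdrawn woman were replaced by one without an event, seven would do (25/180 v 14/180, p = 0.062).

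**4. A borderline result.** 32/180 v 19/180 gives p = 0.049. Losing one control event (31/179) gives 0.064; losing two (30/178) gives 0.083. This case is chosen because it sits next to 0.05.

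**5. False positives under one-sided removal.** Suppose the true rate is 18% in both arms and a share f of SSO women is withdrawn and replaced in one arm only. The observed rate there is p(1 - f)/(1 - pf):

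| f (assumed) | Observed rate | Spurious difference | Chance of a significant result favouring that arm, 180 per arm |
|---|---|---|---|
| 10% | 16.5% | 1.5 points | about 6% |
| 20% | 14.9% | 3.1 points | about 12% |
| 30% | 13.3% | 4.7 points | about 23% |

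The nominal value is 2.5%. The documents supply no value of f; these are scenarios, not estimates.

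**The case against.** The strongest reply is that this route is narrow, and much of that stands.

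- **Item 7 and wound treatment.** A reader might infer that 'other intervention' covers drainage, packing, adjunctive negative pressure or re-operation, so that every surgical incision intervention (SII) triggers exclusion. The documents do not support this. The same phrase governs the 7 days before delivery, where it would bar women given the prophylactic antibiotics that inclusion 8 requires. Section 8.1 plans to collect SII data from the charts of women who return for wound treatment, so they are meant to stay. The likelier meaning is another investigational intervention, which a wound complication would seldom trigger. The post-delivery window still cannot be judged at enrolment.
- **Item 9.** Other entry criteria also lack a time anchor, and the omission does harm only through 7.2. There, withdrawal is discretionary and limited to criteria that preclude further participation. Since what remains is routine visits and chart review, critical illness does not obviously do so. Section 7.1 also separates stopping the dressing early from leaving the study. These points make the event less likely but do not close the route; discretion held by unblinded staff is itself the source of possible bias.
- **Analysis.** Section 9.3 says women who withdraw are still analysed, and 9.4.2 speaks of using all available data. Those sentences conflict with the evaluability sentence without overriding it.
- **Section 9.4.1.** Its phrase "will be calculated for the patients who meet the final inclusion/exclusion criteria" might be read as removing women from the efficacy comparison by later eligibility. The sentence concerns descriptive statistics, and since some criteria are intra-operative, 'final' may simply mean confirmed at the end of surgery. It is not relied on here.
- **A broader route.** Section 7.2 also allows withdrawal for adverse events, a more direct path for a wound complication. The same reconciliation with 9.3 is needed there.

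**Conclusion.** The point holds as a wording defect that should be fixed. Eligibility can operate after randomisation, under unblinded discretion, over the primary-endpoint window, and section 9.3 contradicts itself on whether the woman's recorded event counts. The clearest wound-related route is critical illness from a severe infection; the route through item 7 needs a broad and unlikely reading.

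A reader might infer that a severe wound outcome removes a woman as a matter of course, or that one lost event overturns the trial at its planned size. Neither follows. Withdrawal is permitted, not required, and at 18% v 8% about eight control events must be lost before p exceeds 0.05. One loss decides the result only when it is already borderline, as with 32 v 19.

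The sizes assume a two-sided Pearson test, 180 evaluable women per arm, and removal numbers or shares chosen for illustration. The documents give no frequency for such withdrawals.

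**What to change.** 1. **5.2 item 7:** keep only what can be judged at enrolment, namely investigational treatment in the 7 days before delivery, or current or planned enrolment in another interventional trial through the final visit. Drop the open-ended reference to other interventions.
2. **5.2 item 9:** state that it is read at the time of enrolment.
3. **7.2:** remove a newly developed exclusion as a ground for ending follow-up.
4. **7.2 and 9.3 together:** state one rule. Every randomised woman who had surgery stays in follow-up unless she withdraws consent, and stays in the primary analysis as assigned, with any SSO or SII already recorded. Remove completion of visit 4 as a condition for the intention-to-treat analysis, and say that recruiting a replacement does not take the withdrawn woman out of the data.

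The cost is one wording amendment, with no extra patients or procedures. Treatment decisions are unaffected. The small downside is that a few women who receive another intervention after delivery remain in the analysis.
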